#### **14.3.2.2 Analysis of the other efficacy variables**

Other efficacy variables will be summarized by treatment and visit and will generally be summarized based on imputed data (NRI and multiple imputation [MI] for binary and continuous variables, respectively, unless otherwise stated in the SAP). In some cases, variables may also be summarized based on observed case data (ie, subjects with missing data or who have prematurely discontinued IMP are treated as missing). There may be cases where the multiple imputation model fails to converge. In such situations, the last observation carried forward (LOCF) approach will instead be used to impute the missing data. If LOCF is used instead of multiple imputation for this reason, this will be clearly specified in the corresponding table summary. Should there be no missing data for a study variable, then only observed case data will be presented. Note that for LOCF imputation, any missing data or data collected following

discontinuation of IMP will be imputed with the most recent previous value. See [Section 14.7](#) for further details.

Time to PASI75/90/100 response will be estimated and presented using the Kaplan-Meier product-limit method based on the RS by initially randomized treatment groups (Bimekizumab vs secukinumab). This could make the interpretation of the data challenging given that there are two different bimekizumab dosing regimens starting at Week 16, but it is anticipated that most responses will be observed by Week 16 when all bimekizumab subjects are on the same regimen. Time to a given response will be defined as the length in days from the first dose of IMP until the first date when the response is achieved. Subjects who discontinue IMP prior to achieving a response will be censored at the date of IMP discontinuation. Subjects who reach the Week 48 Visit without achieving the given PASI response will be censored at the date of the Week 48 Visit. The median time to response, including the 2-sided 95% CI, will be calculated for each treatment. Between group differences (bimekizumab vs secukinumab) will be analyzed with the log-rank statistic.

In general, data will be summarized by visit through Week 48 in the double-blind Treatment Period and then by visit in the OLE Period and OLE2 Period separately. All summaries of data up to Week 16 will be based on the RS for the 2 randomized treatment groups (bimekizumab and secukinumab). For visits after Week 16 in the double-blind Treatment Period, by-visit summaries will be prepared for the following 3 groups of subjects:

1. Subjects in the MS summarized by the 3 maintenance treatment groups (bimekizumab 320mg Q4W, bimekizumab 320mg Q8W, and secukinumab). Note that while the MS is primarily defined for the evaluation of data after Week 16, these summary tables will include data at all visits (Baseline to Week 48) to provide a comprehensive summary of subjects by maintenance treatment group for the MS.
2. A subset of Group 1 above. Specifically, this will include only those subjects who are responders at Week 16 for the variable being summarized. This will provide an assessment of how efficacy is maintained among Week 16 responders.
3. Subjects in the RS summarized by the 2 randomized treatment groups (bimekizumab and secukinumab). Data from Baseline to Week 48 will be included in these tables. This provides an intent-to-treat analysis among all randomized subjects in the study through Week 48.

All efficacy variables in the double-blind Treatment Period will be summarized in the manner described for Group 1 and 3 above. Summaries for Groups 2 will be done only for a subset of efficacy variables, namely, PASI75/90/100, IGA Clear or Almost Clear, Scalp IGA Clear or Almost Clear, pp-IGA Clear or Almost Clear, mNAPSI75/90/100, and DLQI 0/1.

In the OLE Period, efficacy variables of interest generally will be summarized descriptively by the combined treatment regimen in the double-blind Treatment Period and re-randomized treatment in the OLE.

In general, efficacy variables will be summarized using descriptive statistics by treatment group and scheduled visit during the OLE Period based on Baseline at beginning of the study unless otherwise specified.

In the OLE2 Period, selected efficacy variables of interest will be summarized descriptively by OLE2 Period Treatment Group during the OLE2 Period.

Further details on the above analyses including analysis in the OLE Period and OLE2 Period will be provided in the SAP.

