- 8b. At Week 28 and all following visits, subjects on continuous treatment for at least 12 weeks with a persistent IGA score  $\geq 3$  over at least a 4-week period are defined as nonresponders and should discontinue IMP.
- 9a. A subject considered as having either a suspected new latent tuberculosis infection (LTBI) or who develops active TB or pulmonary NTMB infection during the study (including but not limited to, conversion demonstrated by IGRA or other diagnostic means) must be immediately discontinued from IMP.

The subject must be permanently withdrawn if further examinations result in a diagnosis of pulmonary NTMB, active TB, or if the subject is diagnosed with LTBI with no initiation of prophylactic treatment, prematurely discontinues prophylactic treatment, or, in the opinion of the Investigator or Sponsor, is noncompliant with prophylactic TB therapy.

Confirmed active TB is an SAE and must be captured on an SAE Report Form and provided to the Sponsor in accordance with SAE reporting requirements. As with all SAEs, periodic follow-up reports should be completed as per protocol requirements until such time as the TB infection resolves.

Additional information on TB policies is provided in [Section 12.3.1](#).

10. Subjects with newly diagnosed inflammatory bowel disease (IBD) or with IBD flares during the study must:
  - Be referred, as appropriate, to a health care professional treating IBD, such as a gastroenterologist
  - Discontinue IMP and be followed-up until resolution of active IBD symptoms

If IBD flares increase in severity or frequency during the study, the Investigator should use clinical judgement in deciding whether the subject should continue in the study and contact the Medical Monitor and UCB study physician to confirm the subject's suitability for continued participation in the study.

11a. Subjects **must be referred** immediately to a mental healthcare professional (eg, locally licensed psychiatrist, psychologist, or master's level therapist) and may be withdrawn from the study based upon the Investigator's judgment of benefit/risk for:

- Active suicidal ideation as indicated by a positive response (“Yes”) to Question 4 of the “Since Last Visit” version of the eC-SSRS.
- Moderately severe major depression as indicated by a PHQ-9 score of 15 to 19 if this represents an increase of 3 points compared to last visit.

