### 14.3 Planned efficacy analyses

#### 14.3.1 Analysis of the primary efficacy variable

The analysis of the primary efficacy variable (PASI100 at Week 16) will be based on the RS. A stratified Cochran-Mantel-Haenszel (CMH) test will be performed, where region and prior biologic exposure (yes/no) will be used as stratification variables. Region and prior biologic exposure have been selected as stratification variables in the analysis because they are stratification variables in the randomization and because they may have an impact on efficacy. Treatment comparisons between bimekizumab and secukinumab will be made based on the CMH test using the p-value for the general association. For the assessment of non-inferiority, a non-inferiority margin of 10% will be used and evaluated based on the CI for the stratified Mantel-Haenszel risk difference between bimekizumab and secukinumab. A non-inferiority margin of 10% has been selected as this is considered to be a clinically relevant difference that could influence the choice of interventions used to treat chronic plaque PSO. Therefore, a difference within the 10% non-inferiority margin would suggest a similar impact on efficacy between the treatments.

Nonresponder imputation (NRI) will be used to account for missing data in the primary analysis. Specifically, any subject who withdraws from IMP prior to Week 16 or who has missing data for the primary efficacy variables at the Week 16 time point will be considered a nonresponder. Based on previous studies of biologics in subjects with moderate to severe chronic plaque PSO,

it is expected that the number of subjects who discontinue prior to Week 16 will be low. For the small percentage of subjects for whom primary endpoint data are unavailable at Week 16, this lack of data is suggestive of an ineffective IMP, thereby supporting the imputation of nonresponse. Therefore, NRI is considered an appropriate method for handling missing data since achieving the clinical response and making it through 16 weeks of IMP are both critical components of the primary outcome.

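### Time to PASI response is censored when study drug stops, although the protocol orders nonresponders to stop, so the late Kaplan-Meier curve overstates cumulative response

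*Protocol*

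**What the plan says.** Protocol Section 14.3.2.2 fixes the analysis in full. Time to PASI75/90/100 response "will be estimated and presented using the Kaplan-Meier product-limit method based on the RS by initially randomized treatment groups". Two censoring rules follow: "Subjects who discontinue IMP prior to achieving a response will be censored at the date of IMP discontinuation", and "Subjects who reach the Week 48 Visit without achieving the given PASI response will be censored at the date of the Week 48 Visit". The arms are then compared: "Between group differences (bimekizumab vs secukinumab) will be analyzed with the log-rank statistic". The only caution given there is that two bimekizumab regimens run in parallel after Week 16.

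Section 6.5, criterion 8b (repeated in the note to Figure 5-1), says who must stop: "At Week 28 and all following visits, subjects on continuous treatment for at least 12 weeks with a persistent IGA score" of 3 or more "over at least a 4-week period are defined as nonresponders and should discontinue IMP".

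The binary PASI endpoints treat stopping differently. Section 14.3.1 counts as a nonresponder "any subject who withdraws from IMP prior to Week 16 or who has missing data for the primary efficacy variables" at Week 16. Section 14.3.2.1 carries nonresponder imputation (NRI) over to the secondary variables, including PASI100 at Week 48.

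Under Sections 8.5 and 8.6, a subject taken off IMP has a Premature End of Treatment visit and then a Safety Follow-Up visit. The latter lists no PASI.

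**The concern.** Kaplan-Meier assumes that a subject censored at a given time has the same later chance of response as those still at risk. Criterion 8b selects subjects for removal because their disease has not responded. Once they are censored, the estimator shares their probability among those who remain, as if they would have gone on to respond at the same rate. No later PASI is scheduled for them, so this is pure assumption.

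Criterion 8b is not the only stop related to outcome. Section 6.5 also withdraws subjects who develop another form of psoriasis, and may withdraw those who use prohibited medication. Neither of these waits until Week 28.

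At stake is the reported cumulative response curve, mainly after Week 28, and possibly the comparison of the arms if they lose very different numbers of failures.

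**Working it through.** **Inputs from the protocol.** 350 subjects per arm; PASI100 at Week 16 of 60% and 44% (Section 14.9); the visit schedule to Week 48; criterion 8b active from Week 28.

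**Assumed, because the protocol gives no figure.** First PASI100 response accrues linearly to 60% / 44% by Week 16 and to 75% / 60% by Week 48. Early stops are spread evenly over Weeks 4, 8, 12, 16, 20 and 24. Stops under 8b are spread evenly over Weeks 28, 32, 36, 40 and 44. All stoppers are subjects who would not have responded.

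**The plan's own figure.** There is none for time to response. The stated 98% superiority power checks the response rates and sample size. Pooled SE = √(0.52 × 0.48 × 2/350) = 0.03777. Unpooled SE = √(0.60 × 0.40/350 + 0.44 × 0.56/350) = 0.03728. Power = Φ[(0.16 − 1.96 × 0.03777)/0.03728] = Φ(2.31) = 98.9%, which agrees.

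**Formula.** Let e be the share of randomized subjects first responding at a visit, R the share at risk just before it, and q the share censored at it. Then S is multiplied by (1 − e/R), and the next R is R − e − q. If stoppers stay at risk to Week 48, q = 0 until then, and 1 − S equals the sum of the e terms, which is the proportion of randomized subjects who respond.

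**Worked case: bimekizumab, 10% stopped under 8b (q = 0.02 at each of five visits).** After Week 16, e = (0.75 − 0.60) × 4/32 = 0.01875 per visit.

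| Week | R | 1 − S, protocol rule | Actual response |
|---|---|---|---|
| 28 | 0.36250 | 65.6% | 65.6% |
| 32 | 0.32375 | 67.6% | 67.5% |
| 36 | 0.28500 | 69.7% | 69.4% |
| 44 | 0.20750 | 74.6% | 73.1% |
| 48 | 0.16875 | 77.4% | 75.0% |

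The excess at Week 48 is 2.4 points.

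**All scenarios, 1 − S at Week 48 under the protocol rule** (actual response: 75.0% bimekizumab, 60.0% secukinumab):

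| Early stops | 8b stops | Bimekizumab | Secukinumab |
|---|---|---|---|
| 0 | 2% | 75.4% | 60.3% |
| 0 | 5% | 76.0% | 60.7% |
| 0 | 10% | 77.4% | 61.5% |
| 5% | 5% | 79.1% | 62.8% |
| 5% | 10% | 81.1% | 63.9% |
| 10% | 10% | 86.6% | 66.7% |

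At Week 16, 8b adds nothing. Early stops of 5% to 10% add 0.7 to 2.2 points there. The median falls at the same visit under both rules in every scenario (Week 16 for bimekizumab, Week 28 for secukinumab).

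**Gap between arms at Week 48.** The true gap is 75.0 − 60.0 = 15.0 points. Stops are given as early/8b, bimekizumab then secukinumab:
- 3%/1% and 3%/5%: 14.8 points
- 5%/1% and 5%/10%: 14.0 points
- 5%/2% and 10%/10%: 11.5 points

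**Log-rank.** In 600 simulated trials of 350 per arm, the mean z was as follows (protocol rule, then stoppers kept to Week 48):
- First pattern above: 4.41 and 4.40
- Second pattern above: 4.47 and 4.51
- Equal true response in both arms (52% by Week 16, 68% by Week 48), 3% early stops in each and 8b stops of 1% v 10%: −0.36 and −0.04. The shift favours the arm with more stopped failures.

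**The case against.** The case for leaving this alone is substantial.

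- **Small effect of 8b.** It starts only at Week 28 and needs persistent IGA of 3 or more, which is narrower than lacking PASI90 or PASI100. Section 14.3.2.2 expects most responses by Week 16, and Section 14.3.1 expects few discontinuations before then. This stands. The larger figures above depend on assumed early stopping.
- **A different question.** Censoring at discontinuation asks what would happen on continued treatment. Section 14.7 also includes a missing-at-random multiple imputation with that aim. The plurality of approaches is legitimate. But the on-treatment question still needs censoring unrelated to prognosis, and 8b stoppers are chosen for poor prognosis. In the scenarios above no stopper would have responded, so 75% and 60% are the on-treatment values too. If some stoppers would have responded, part of the excess would be a difference of estimand and not bias.
- **NRI results are already planned.** PASI100 at Week 48 is tested on the Randomized Set with NRI, and by-visit summaries run to Week 48. This stands, but no first-response curve is planned on that basis.

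A reader might infer that the time-to-response and NRI analyses contradict each other. They do not. They are inconsistent in approach, and the Section 14.3.1 rule concerns withdrawal before Week 16, whereas 8b acts from Week 28. A reader might also infer that the medians and the log-rank comparison are materially biased, or that stopping is known to differ by arm. The calculations do not show the first, and the protocol gives no rates by arm.

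**Conclusion.** The point holds as a limited one. Censoring is informative by the protocol's own stopping rule, and nothing else in the protocol corrects it. The late Kaplan-Meier curve therefore overstates the proportion of randomized subjects who respond. The excess at Week 48 is about 0.3 to 2.4 points with 8b stops alone in 2% to 10% of subjects, and about 3 to 12 points when early unresponded stops of 5% to 10% are added. These sizes rest on assumed stopping rates, assumed Week 48 responses and stoppers who would not have responded.

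Medians did not move, and the log-rank test hardly did under the assumed treatment effect. Strongly unequal stopping can bias the comparison.

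It would be wrong to read this as a threat to the trial's main result. Time to response is listed among the other efficacy variables in Section 4.3.1 and lies outside the fixed testing sequence, so the primary conclusion and the familywise error rate are untouched. The change is still worth making because it is cheap and the rule is fixed in the protocol text.

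**What to change.** Replace the discontinuation sentence in Section 14.3.2.2 with one to this effect: *subjects who discontinue IMP before achieving the given response are kept as nonresponders and censored at Week 48*. Reporting the cumulative incidence of response with IMP discontinuation as a competing event is equivalent. Either version follows the NRI principle used for the binary PASI endpoints. Criterion 8b itself stays as it is.

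The log-rank test can be run on the data so defined, so Gray's test is optional. The present Kaplan-Meier analysis may remain as a sensitivity analysis, labelled as describing response had treatment continued and as assuming uninformative discontinuation.

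The cost is one sentence and a matching change in programming, with no new data. Reported response percentages will be slightly lower, and a median may not be reached.

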## **14.4 Subgroup analyses**

Subgroup analyses will be performed on the primary and secondary efficacy variables that are part of the fixed sequence testing procedure described in [Section 14.2](#). The following variables for subgroup analyses will be defined: age, gender, disease duration, region, weight, body mass index, prior systemic chemotherapy or phototherapy, prior biologic exposure, prior primary failure to biologics, prior systemic therapy of any kind, Baseline disease severity, and antibody positivity. These summaries will be based on imputed data (NRI) and will include descriptive statistics only.

## **14.5 Planned safety and other analyses**

### **14.5.1 Safety analyses**

Safety variables will be analyzed for all subjects in the SS. This will include all subjects who took at least one dose of study medication. Selected analyses will also be presented for MS, OLS, and OL2S. Adverse events will be coded according to the Medical Dictionary for Regulatory Activities. Adverse events will be summarized descriptively by treatment group, primary system organ class, High Level Term (HLT), and PT. Additional tables will summarize AEs by intensity and relationship to IMP, AEs leading to withdrawal from the study, SAEs, and deaths. Safety topics of interest will be summarized and will be described in greater detail in the SAP.

Laboratory values (including markedly abnormal laboratory values), urinary values, vital signs, and extent of exposure will be presented descriptively by treatment group. Definitions for markedly abnormal laboratory values will be provided in the SAP.

### **14.5.2 Pharmacokinetic analyses**

Pharmacokinetic variables will be analyzed for all subjects in the PK-PPS. Bimekizumab plasma concentrations will be summarized for each treatment at each scheduled visit where samples are collected.

### **14.5.3 Immunogenicity analyses**

Anti-bimekizumab antibodies will be assessed using a tiered approach: screening, confirmatory, and titer assays will be used. Anti-bimekizumab antibodies (including positivity) will be summarized by treatment at each scheduled visit at which samples are collected.

## **14.6 Handling of protocol deviations**

Important protocol deviations are deviations from the protocol which potentially could have a meaningful impact on study conduct, or on the primary efficacy, key safety, or PK/PD outcomes for an individual subject. The criteria for identifying important protocol deviations will be defined within the appropriate protocol-specific document at study start. Important protocol deviations will be reviewed as part of the ongoing data cleaning process and all important deviations will be identified and documented prior to unblinding to confirm exclusion from analysis sets.

---

## 14.7 Handling of dropouts or missing data

Study variables with multiple components may have rules to account for partial missing data of 1 or more components. Such rules will be defined in the SAP. The following rules are outlined for cases where variables are completely missing, including partial missing data where the data handling rules conclude that the variable should be treated as completely missing.

The analysis of the primary efficacy variable will use NRI for handling of missing data. That is, subjects with missing data or who have discontinued IMP prior to Week 16 will be considered as nonresponders for the primary analysis.

The following sensitivity analyses for the primary efficacy variable will be performed:

1. Missing data will be addressed by using MI (Markov-Chain Monte Carlo method for intermittent missing data, followed by monotone regression for monotone missing data) to evaluate the effect of the method for handling missing data on the analysis. The actual PASI scores will be imputed and then dichotomized to obtain the response status. The treatment differences for each imputed data set will subsequently be evaluated using the stratified CMH test as used in the primary analysis. The results from each of the imputed data sets will be combined for overall inference using Rubin's rules, which account for the uncertainty associated with the imputed values (Rubin, 1987). This will be done using SAS PROC MIANALYZE. This procedure assumes a missing at random pattern of missingness and corresponds to an estimand of the difference in outcome improvement if all subjects tolerated or adhered to treatment (Mallinckrodt et al, 2012). This is an estimand of efficacy to evaluate the de jure hypothesis.
2. Another sensitivity analysis will be based on observed data at Week 16. Subjects with missing data or who have prematurely discontinued IMP will be treated as missing. The same stratified CMH test as in the primary efficacy analysis will be used.

Further details on the MI procedures will be provided in the SAP.

Missing data for the secondary efficacy variables (which are all binary) will be imputed using NRI. Additionally, the 2 missing data-handling approaches described above for the primary efficacy variable will be used for the secondary efficacy variables. Additional missing data handling approaches may be described in the SAP.

For other continuous efficacy variables, MI will be used to impute missing data when possible. If the imputation model cannot converge, LOCF will be used. The MI procedure will be similar to sensitivity analysis #1 described above with the following differences: (1) the imputation model will use the change from Baseline (instead of actual) values by visit and no dichotomization will be necessary; (2) instead of using the stratified CMH test, the imputed data sets will be combined and simple means and standard errors will be calculated using Rubin's rules (via SAS PROC MIANALYZE). For calculation of other descriptive statistics such as the median, minimum and maximum, Rubin's rules do not apply. Multiple imputation estimates will be computed by simply averaging the estimates from the multiple repetitions of the imputation algorithm.

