## **4 STUDY VARIABLES**

### **4.1 Primary efficacy variable**

The primary efficacy variable is the PASI100 response, defined as complete clearance from Baseline in the PASI score, at Week 16.

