### **9.1 Psoriasis Area Severity Index**

The PASI is the most commonly used and validated assessment for grading the severity of PSO in clinical studies (Feldman, 2004). The PASI quantifies the severity and extent of the disease and weighs these with the percentage of BSA involvement.

The percent area of involvement (BSA%) is estimated across 4 body areas; head, upper extremities, trunk, and lower extremities. Assessors will enter the degree of involvement for a given region on a scale of 0 to 6 (0=none; 1=1% to <10% affected, 2=10% to <30% affected, 3=30% to <50% affected, 4=50% to <70% affected, 5=70% to <90% affected, 6=90% to 100% affected) (Table 9-1).

The Investigator assesses the average redness, thickness, and scaliness of lesions in each body area (each on a 5-point scale); 0=none, 1=slight, 2=moderate, 3=marked, and 4=very marked.

The PASI score ranges from 0 to 72 with a higher score indicating increased disease severity.

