**Table 9-1: Body areas for calculation of percent BSA for PASI**

| Body area         | Details of area  | BSA  | Degree of involvement of body area a |
|-------------------|--|------|---|
| Head              | Face, back of head   | 10%  | 0 to 6  |
| Upper extremities | Left, right, upper lower, flexor surface, extensor surface                     | 20%  | 0 to 6  |
| Trunk             | Front, back, groin   | 30%  | 0 to 6  |
| Lower extremities | Left, right, upper lower, flexor surface, extensor surface, including buttocks | 40%  | 0 to 6  |
| Total             |  | 100% |   |

BSA=body surface area; PASI=Psoriasis Area and Severity Index

a Where 0=none; 1=1% to <10% affected; 2=10% to <30% affected; 3=30% to <50% affected; 4=50% to <70% affected; 5=70% to <90% affected; 6=90% to 100% affected

The PASI75, PASI90, and PASI100 responses are based on at least 75%, 90%, and 100% improvement in the PASI score, respectively.

The total BSA affected by PSO will be entered as a percentage from 0 to 100.

The PASI will be completed at the visits specified in Table 5-1, Table 5-2, and Table 5-3.

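### The missing-at-random sensitivity analysis for PASI100 imputes a continuous score and cuts it at the scale floor, so it understates clearance in imputed subjects and leans toward nonresponder imputation

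*Protocol*

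**What the plan says.** Section 4.1 sets the endpoint: "The primary efficacy variable is the PASI100 response, defined as complete clearance from Baseline in the PASI score, at Week 16". Section 9.1 gives the scale, "The PASI score ranges from 0 to 72", and the text below Table 9-1 gives the response rule: "The PASI75, PASI90, and PASI100 responses are based on at least 75%, 90%, and 100% improvement in the PASI score, respectively". A PASI100 responder is thus a subject at the floor of the scale.

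The primary analysis counts missing subjects as nonresponders. Sensitivity analysis 1 in Section 14.7 replaces this by multiple imputation, using a "Markov-Chain Monte Carlo method for intermittent missing data, followed by monotone regression for monotone missing data". It then says: "The actual PASI scores will be imputed and then dichotomized to obtain the response status". The imputed data sets go through the stratified Cochran-Mantel-Haenszel test and are combined by Rubin's rules. The section describes this as a missing-at-random analysis whose estimand is the treatment difference under full adherence.

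The approach is also carried further: "the 2 missing data-handling approaches described above for the primary efficacy variable will be used for the secondary efficacy variables". That includes PASI100 at Week 48. Further detail on the imputation is left to the SAP.

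**The concern.** Imputing a score and cutting it afterwards works when the score is roughly continuous around the cut-off. Here the cut-off is the lower end of a bounded scale, and the plan itself expects about half of all subjects to sit exactly on it. A linear regression imputation treats the score as a mean plus normal noise. It puts no mass at 0, spreads draws over negative and small positive values, and sets the share at or below 0 by the normal tail instead of the observed clearance rate.

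At stake is the purpose of the analysis. Section 14.3.1 defends NRI on the ground that missing data suggest an ineffective treatment. Sensitivity analysis 1 is the planned model-based test of that choice. If it under-predicts clearance in the subjects it imputes, its agreement with NRI is partly produced by the method and is weaker evidence of robustness than it appears.

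**Working it through.** **Inputs from the protocol.** PASI100 rates p of 0.60 and 0.44, and 350 per arm (Section 14.9); two-sided alpha 0.05 (Section 14.2); range 0 to 72 and the response rule (Section 9.1). Section 14.3.1 expects few discontinuations before Week 16 but gives no figure.

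**Assumed.** Coefficient of variation c of the non-zero PASI scores, 0.5 to 2; equal missing shares of 3%, 5% and 10% in both arms.

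**1. The plan's own figure.** Power = Φ[(0.16·√350 − 1.96·√(2·0.52·0.48)) / √(0.60·0.40 + 0.44·0.56)] = Φ[(2.993 − 1.385)/0.697] = Φ(2.306) = 98.9%, against the stated 98%. The inputs are read correctly.

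**2. Share of normal draws at or below 0.** Let PASI be 0 with probability p and otherwise positive with mean m and SD c·m. Then the mean is (1−p)m and the variance is (1−p)m²(c²+p). A normal distribution with that mean and variance falls at or below 0 with probability Φ(−√[(1−p)/(c²+p)]), which does not depend on m. At c = 1: Φ(−√(0.40/1.60)) = Φ(−0.50) = 0.309 for bimekizumab, and Φ(−√(0.56/1.44)) = Φ(−0.624) = 0.266 for secukinumab.

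| c | Bimekizumab (correct 0.60) | Ratio | Secukinumab (correct 0.44) | Ratio |
|---|---|---|---|---|
| 0.5 | 0.246 | 0.41 | 0.184 | 0.42 |
| 1 | 0.309 | 0.51 | 0.266 | 0.61 |
| 1.5 | 0.354 | 0.59 | 0.324 | 0.74 |
| 2 | 0.384 | 0.64 | 0.361 | 0.82 |

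Because mean PASI is above 0, this share is always below 0.5. The bimekizumab ratio therefore stays below 0.5/0.60 = 0.83 whatever c is.

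**3. With earlier visits in the model.** Simulation: 350 per arm, six visits, 10% monotone missing completely at random, sequential Bayesian linear regression within arm, c from 0.75 to 1.5, between-visit correlation parameter 0.6 to 0.9. Ratios were 0.51 to 0.63 on bimekizumab and 0.56 to 0.78 on secukinumab. Conditioning on earlier scores does not repair the problem.

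**4. Other comparison rules.** Requiring exact equality to 0, or keeping draws strictly above 0, gives no imputed responder. Rounding to 0.1 and requiring 0 gives 1% to 2%.

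**5. Effect on the Week 16 difference.** Arm rate = p·(1 − missing share) + imputed rate·(missing share). At 5% missing and c = 1: 0.60·0.95 + 0.309·0.05 = 0.5854 and 0.44·0.95 + 0.266·0.05 = 0.4313, a difference of 0.1541.

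| Missing | Correct under missing at random | Draws at or below 0 respond (c = 1) | No imputed responder (same as NRI) |
|---|---|---|---|
| 3% | 16.0 | 15.6 | 15.5 |
| 5% | 16.0 | 15.4 | 15.2 |
| 10% | 16.0 | 14.8 | 14.4 |

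With the formula of step 1, and ignoring between-imputation variance, power at the rates in the third column is 98.4% (5% missing) and 97.65% (10%).

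**6. PASI90.** In the same simulation the imputed PASI90 share was 0.56 to 0.71, against a true 0.69 to 0.86. PASI90 is affected too, less strongly.

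**The case against.** **The SAP may settle it.** Section 14.7 defers further imputation detail and never uses the word normal. Predictive mean matching also imputes PASI scores and then dichotomizes them, so for the monotone part it could be argued to fit the text. That part stands: some of the repair could be made in the SAP. But the protocol does fix the methods, the imputed quantity and the order of steps. With ordinary regression draws, the open choices on bounds, rounding and negative draws only move the result between no responders and the shares in step 2. The Markov-chain step for intermittent gaps leaves less room still.

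**Are all imputed subjects nonresponders?** A reader might infer that this is NRI under another name. The documents do not support that. The response rule asks for at least 100% improvement, which a draw at or below 0 satisfies, and setting negative draws to 0 also makes them responders. The 0 to 72 range describes the instrument and is not a stated bound on imputed values. The total loss in step 4 needs a rule that the protocol does not contain.

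**Is the chance halved in both arms?** Halving is a fair description for bimekizumab at c = 1. For secukinumab the ratio runs from 0.42 to 0.82, so no single figure serves both arms.

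**It is only a sensitivity analysis, and not the only one.** This stands. Sensitivity analysis 2 uses observed data without imputation and does not share the flaw. It is not a full substitute, because it ignores the earlier PASI scores of subjects who drop out.

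**Conclusion.** The point holds, at modest size. As specified, sensitivity analysis 1 cannot reproduce the PASI100 probability under missing at random. With draws at or below 0 counted as response, imputed subjects get roughly 0.4 to 0.65 of the correct probability on bimekizumab and 0.4 to 0.8 on secukinumab. The analysis is pulled toward NRI and does not estimate what Section 14.7 says it estimates.

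This rests on reading the named methods as normal-theory regression and on an assumed spread of non-zero PASI. The differences in step 5 also assume equal missing shares in the two arms. With unequal shares the difference need not shrink: 5% missing on bimekizumab and 10% on secukinumab at c = 1 gives 0.5854 − 0.4226 = 0.1628.

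A reader might go on to infer that the superiority claim is in doubt. It is not: the primary analysis is NRI, and the Week 16 difference moves by 0.6 points at 5% missing and 1.2 points at 10%. The same flaw carries to PASI100 at Week 48. Its size there depends on dropout, and the protocol gives neither a Week 48 response rate nor a dropout figure, so none is computed here.

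**What to change.** In Section 14.7, for PASI100, replace normal-draw imputation by a method that can return exact zeros, and state that it covers both intermittent and monotone gaps. Either of two options would do:

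- Impute response status by logistic regression (monotone or fully conditional specification), separately by arm, with earlier PASI and response status, region and prior biologic exposure as predictors.
- Use predictive mean matching on PASI, which draws observed values including zeros.

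Combine the stratified Mantel-Haenszel results with Rubin's rules. Apply the same method to PASI100 at Week 48 and PASI90 at Week 16. Nothing computed here supports requiring it for PASI75 at Week 4 or IGA 0/1 at Week 16.

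The cost is a sentence or two in Section 14.7, matching SAP text and minor programming. Data collection, sample size and the primary analysis are unaffected.
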